6.5. Clinical Measurements

6.5.1. Clinic Visits

Clinic visits will include evaluations of height (Visit I only), BMI calculation (Visit I and 2 only), vital signs, prior and concomitant medication/supplement use, and inclusion/exclusion criteria (for eligibility at visit I and for potential protocol deviations at subsequent visits). In order to calculate BMI, height will be measured at the screening visit (Visit I, week -I) using a wall-mounted stadiometer. Participants will remove shoes prior to height measurement.

Standardized vital signs measurements will include resting blood pressure and heart rate measured using an automated blood pressure measurement device. Blood pressure will be obtained after the participant has been sitting for at least five min. Systolic and diastolic pressures will be measured once using an appropriate sized cuff (bladder within the cuff must encircle 2:80% of the arm). Clinic staff may take a second blood pressure and heart rate, if warranted. In the event a second measure is assessed, the second measurement will be recorded

in the eCRF. Should elevated blood pressure (see Section 6.3.2, criterion 13) be present at the screening visit (Visit 1, week -1), one retest will be allowed on a separate day, prior to Visit 2 (week 0).

Additionally, AEs will be assessed at each post-randomization visit (Visits 2, 3, 4, 5, 6, and 7; weeks 0, 2, 4, 8, 12, and 16). Inquiring about AEs will occur with an open-ended question. This study is a dietary intervention and does not include an investigational study drug or product. However, for safety purposes, assessment of AEs will be conducted in a manner consistent with clinical trials on investigational study drugs or products. Participants will be asked an open-ended question (e.g. "Have there been in any changes in your health or medications since you were last asked?").

6.5.2. Laboratory Measurements

The procedures for all clinical laboratory measurements will be described in detail in a laboratory manual. Laboratory parameters that are missing or have not been obtained must be entered in the eCRF as "not done."

The following will be performed as a part of the fasting $(12 \pm 2 h)$ chemistry profile at Visit I (week -I): glucose, calcium, albumin, total protein, sodium, potassium, C02, chloride, BUN, creatinine, ALP, AST, ALT, total bilirubin, and osmolality. Analytes will be assessed by Elmhurst Memorial Reference Laboratory (Elmhurst, IL).

The following will be performed as part of the fasting $(12 \pm 2 h)$ hematology measurements at Visit I (week -1): white blood cell count/automated differential, red blood cell count, hemoglobin, hematocrit, platelet count, mean corpuscular volume, mean corpuscular hemoglobin, and mean corpuscular hemoglobin concentration. Analytes will be assessed by Elmhurst Memorial Reference Laboratory (Elmhurst, IL).

At Visits 2 and 7 (weeks 0 and 16) samples will be collected for the assessment ofhs-CRP. hs-CRP will be assessed by Elmhurst Memorial Reference Laboratory (Elmhurst, IL). Additional samples will be collected and stored and archived for possible future analysis of non-genetic indicators of inflammation and metabolism.

An in-clinic urine pregnancy test will be performed at Visits I, 2, 4, 5, 6, and 7 (weeks -1, 0, 4, 8, 12, and 16) for females < 60 years of age.

6.5.3. Gown Body Weight Assessment

Body weight will be measured at all visits (Visits I through 7; weeks -1 through 16) following a fast (12 ± 2 h, water only). Participants will be asked to change into a gown and remove their shoes before their weight is obtained. Weight will be recorded on a medical quality digital scale (Health O Meter 349KLX) to the nearest tenth pound (one decimal place). The same digital scale will be used to measure body weight at each clinic visit. The scale will be calibrated at least yearly to assess accuracy.

Confidential

6.5.4. Anthropometric Measurements

Measurements of waist, hip, chest, dominant upper arm, and dominant thigh circumferences will be conducted at Visits 2, 4, 5, 6, and 7 (weeks 0, 4, 8, 12, and 16; Appendix 2). A stretch-resistant anthropometric tape (Gulick 11 model #67020, Gays Mills, WI) with an indicator buckle to denote proper amount of tension applied to the tape will be used for body circumference measurements. These measurements will be used for calculation of total body circumference and waist-to-hip ratio.

6.5.5. Dual-Energy X-ray Absorptiometry

DXA scans (GE Lunar Prodigy, enCORE software version 16, Madison, WI) will be performed on Visits 2, 4, 5, 6, and 7 (weeks 0, 4, 8, 12, and 16) to assess body composition. The DXA scan will provide estimates of total body fat mass, total body fat-free mass, trunk fat, and non-trunk fat. Female participants <60 years of age must have a negative pregnancy test before the DXA scan is initiated.

6.5.6. Impact of Weight on Quality of Life-Lite Questionnaire

Participants will be administered the electronic IWQOL-Lite Questionnaire at Visits 2, 5, and 7 (weeks 0, 8, and 16; Appendix 3) to assess obesity specific QoL domains (physical function, selt esteem, sexual life, public distress and work).

6.5.7. RAND-36 Questionnaire

Participants will be administered the electronic RAND-36 Questionnaire at Visits 2, 5, and 7 (weeks 0, 8, and 16; Appendix 4). This widely used 36-item test requires participants to assess eight health concepts: physical functioning, role limitations caused by physical health problems, role limitations caused by emotional problems, social functioning, emotional well-being, energy/fatigue, pain, and general health perceptions.

6.5.8. l'rogram Questionnaire

Participants will be administered the electronic Program Questionnaire at Visits 2, 4, 5, 6, and 7 (weeks 0, 4, 8, 12, and 16; Appendix 5). The questionnaire will include questions about activity level only (Question 1 and 2) at Visit 2 (week 0).

Based on the answers to \blacksquare and 2, the Physical Activity Level (PAL = ratio of total energy expenditure *I* resting metabolic rate) can be determined as shown in each cell for each combination of work/school and leisure time activity estimates. This value can then be recorded for each participant at each time point during the study to track physical activity.

		Very Light	Light	Moderate	Active	Very Active
0	Very Light	1.4	1.5	1.6	1.7	1.9
8 	Light	1.5	1.6	1.7	1.8	2.0
:;at) <	Moderate	1.6	1.7	1.8	1.9	2.2
15	Heavy	1.7	1.8	1.9	2.1	2.3

At Visits 4, 5, 6, and 7 (weeks 4, 8, 12, and 16), participants in all groups will be asked to document their adherence to the weight loss plan and activity level over the previous 4-week period (Questions 3, 4 and 5), and participants in the TSFL and MEDD groups will also be asked to assess their adherence to study meal replacement intake (Question 6).

6.5.9. Satisfaction and Health/Well-being Questionnaire

Participants will complete the electronic Satisfaction and Health/Well-Being Questionnaire at Visit 7 (week 16; Appendix 6). The Satisfaction and Health/Well-Being Questionnaire is a 20-item questionnaire assessing participant satisfaction with the assigned diet program and general health/well-being. Question order will be randomized.

6.6. Procedures at Each Clinic Visit

6.6.1. Screening (Visit I, week -1) (-2 weeks to -1 day)

- Informed consent/HIPAA
- Demographics/medical history
- Clinic visit
 - Height
 - BMI calculation
 - Vital signs
 - Review inclusion/exclusion criteria
 - Assess prior and current medication/supplement use
 - Gown body weight
- In-clinic urine pregnancy test, where applicable
- Chemistry profile
- Hematology panel

6.6.2. Baseline (Visit 2, week 0) (1 to 14 days alter Visit 1)

- Clinic visit
 - BMI Calculation
 - Vital signs
 - Assess AEs
 - Review inclusion/exclusion criteria

Confidential

- Assess concomitant medication/supplement use
- Randomization
- hs-CRP
- Archived blood samples
- Gown body weight
- Anthropometric measurements
- In-clinic urine pregnancy test, where applicable
- DXA
- Program Questionnaire
- IWQOL-Lite Questionnaire
- RAND-36 Questionnaire
- Diet education and handouts (Control group)
- Dispense packet of educational materials (TSFL and MEDD groups)
- Dispense starter meal kits (TSFL and MEDD groups)
- Schedule initial TSFL coaching session (TSFL group only)
- Reminder to call Nutrition Support Team (MEDD group only)
- Order study foods (TSFL and MEDD groups)

6.6.3. Clinic visit (Visit 3, week 2 ± 2 d)

- Clinic visit
 - Vital signs
 - Assess AEs
 - Review inclusion/exclusion criteria
 - Assess concomitant medication/supplement use
- Gown body weight

6.6.4. Clinic visit (Visit 4, week 4 ± 3 d)

- Clinic visit
 - Vital signs
 - Assess AEs
 - Review inclusion/exclusion criteria
 - Assess concomitant medication/supplement use
- Gown body weight
- Anthropometric measurements
- In-clinic urine pregnancy test, where applicable
- DXA
- Program Questionnaire
- Order study foods (TSFL and MEDD groups)

6.6.5. Clinic visit (Visit 5, week 8 ± 3 d)

- Clinic visit
 - Vital signs
 - Assess AEs
 - Review inclusion/exclusion criteria
 - · Assess concomitant medication/supplement use

- Gown body weight
- Anthropometric measurements
- In-clinic urine pregnancy test, where applicable
- DXA
- Program Questionnaire
- IWQOL-Lite Questionnaire
- RAND-36 Questionnaire
- Order study foods (TSFL and MEDD groups)

6.6.6. Clinic visit (Visit 6, week 12 ± 3 d)

- Clinic visit
 - Vital signs
 - Assess AEs
 - Review inclusion/exclusion criteria
 - Assess concomitant medication/supplement usc
- Gown body weight
- Anthropometric measurements
- In-clinic urine pregnancy test, where applicable
- DXA
- Program Questionnaire
- Order study foods (TSFL and MEDD groups)

6.6.7. Clinic visit (Visit 7, week $16 \pm 3d$)

- Clinic visit
 - Vital signs
 - Assess AEs
 - Review inclusion/exclusion criteria
 - Assess concomitant medication/supplement use
- Gown body weight
- Anthropometric measurements
- In-clinic urine pregnancy test, where applicable
- hs-CRP
- Archived blood samples
- DXA
- Program Questionnaire
- IWQOL-Lite Questionnaire
- RAND-36 Questionnaire
- Satisfaction and Health/Well-being Questionnaire
- Provide instructions for placing study food orders (control group completers only)
- Dispense Group-specific Maintenance Materials and Guides

In addition to (and outside o1) the regularly scheduled clinic visits described above, the TSFL Group will receive telephone coaching sessions per the schedule outlined in the TSFL Group-Specific Procedures (see page 18).

6.7. Early Termination Procedures

The term "Early Termination" refers to a participant's non-completion of the study. Should a participant decide to withdraw, all efforts will be made to complete and report observations as thoroughly as possible. In the event that a participant is withdrawn from the study, the reason for the withdrawal and the party who initiated the withdrawal (participant or Clinical Investigator) will be documented. Should the participant decide to withdraw, documentation of the early termination will be made and an attempt to conduct an early termination visit (which will occur at week 16 and include the clinic visit procedures for Visit 7).

The primary reason for a participant withdrawing prematurely should be selected fiom the following standard categories:

Adverse Event- event which results in discontinuation of the study food by the participant or that in the judgment of the Clinical Investigator for the best interest of the participant requires discontinuation of study food (includes all categories of study food relatedness; Not Related, Unlikely, Possibly, Probably, and Definitely).

Death -death of the participant.

Withdrawal of Consent- participant desires to withdraw from further participation in the study in the absence of a medical need to withdraw determined by the Clinical Investigator.

Lost to Follow-Up- participant did not return for one or more follow-up visit(s) following dispensing of test product and could not be contacted thereafter. The reason for withdrawal was unknown and could not be documented.

Other- causes of premature termination from the study other than the above, such as theft or loss of study foods, pregnancy, termination of study by Sponsor, etc.

6.8. Procedure for Participants that Reach a Low BMI

Participants who achieve a BMI of 19.0 kg/m² or below will discontinue their assigned weight loss diet and this will be noted in source documents. Participants will receive maintenance materials and guides (appropriate to their assigned study group) and will be asked to follow a weight maintenance plan for the duration of the study. The participant will continue in the study and be asked to return for remaining clinic visits.

7. Assessment of Outcomes

7.1. Primary Outcome Variable

The primary endpoint is body weight and the primary outcome is change (percent and absolute change) from baseline (Visit 2; week 0) body weight to Visit 7 (week 16). Body weight change (percent and absolute change) at Visits 3, 4, 5, and 6 (weeks 2, 4, 8, and 12) will also be evaluated.

7.2. Secondary Outcome Variables

Secondary outcome variables will include the following:

- Proportion of participants achieving 2:5% and 2:10% loss of baseline body weight at each post-randomization visit (Visits 3, 4, 5, 6, and 7; weeks 2, 4, 8, 12, and 16)
- Percent and absolute change in body composition parameters (measured via DXA) from baseline to Visits 4, 5, 6, and 7 (weeks 4, 8, 12, and 16).
 - o Total fat mass
 - o Total lean mass (non-bone fat free mass)
 - o Percent body fat (expressed as a percentage of total body mass)
 - o Percent lean mass (expressed as a percentage of total body mass)
 - o Android fat and lean mass
 - o Gynoid fat and lean mass
 - o Abdominal visceral fat mass and volume
- Absolute change in body circumference parameters from baseline to Visits 4, 5, 6, and 7 (weeks 4, 8, 12, and 16).
 - o Waist circumference
 - o Hip circumference
 - o Chest circumference
 - o Dominant upper ann circumference
 - o Dominant thigh circumference
 - o Total body circumference (sum of all 5 measures)
 - o Waist:hip ratio
- Absolute change in QoL questionnaire outcomes (total and domain scores) from baseline to Visits 5 and 7 (weeks 8 and 16). QoL will be measured using both the RAND-36 Questionnaire [which uses the same questions as the Short Form (36) Health Survey Questionnaire (Ware JE, eta!. 1992)] and the IWQOL-Lite Questionnaire.
 - The IWQOL-Lite Questionnaire (Kolotkin RL, eta!. 2001) is a 31-question self-report instrument to assess obesity specific quality of life and consists of five domains: Physical Function (11 questions), SelfEsteem (7 questions), Sexual Life (4 questions), Public Distress (5 questions), and Work (4 questions).
 - The RAND 36-Item Health Survey Questionnaire assesses eight health domains: physical functioning (10 questions), role limitations due to physical health problems (4 questions), bodily pain (2 questions), general health perceptions (5 questions), vitality (4 questions), social functioning (2 questions), role limitations due to emotional problems (3 questions), and emotional well-being (5 questions) (RAND HEALTH, 2009).
- Weight loss program adherence assessed at Visits 4, 5, 6, and 7 (weeks 4, 8, 12, and 16) based on the Program Questionnaire.
 - Adherence will be calculated based on self-reported TSFL/MEDD meal replacement product consumption, participation at assigned coaching sessions (TSFL only), utilization of Nutrition Support (TSFL/MEDD), and a single question VAS rating adherence to their assigned weight loss program (all groups).
- Participant satisfaction and health/well-being assessed via the Satisfaction and Health/Well-being Questionnaire at Visit 7 (week 16).
- Absolute change in hs-CRP from baseline (Visit 2; week 0) to Visit 7 (week 16).

Jason Pharmaceuticals, Inc. BI0-1607 (MED 019) 21 June 2016; Version 1.7 1012 CT 1022 CT

8. Data Analysis and Statistical Methods

8.1. Sample Size

A standard deviation of 15.0 lb for change in body weight over 16 weeks was derived from the largest variability observed in a previous study by Davis et al. (2010) that compared weight loss over 16 weeks on the Mcdifast 5 & I Plan@ (-29.8 \pm 13.0 lb) vs. a food-based isocaloric control diet (-14.3 \pm 15.0 lb). Using this estimate of expected variability and accounting for a more conservative mean difference in weight loss between groups over a similar timefi'ame, an evaluable sample of 55 participants in each group (165 total) will provide 80% power to detect a difference of 9.0 pounds (an effect sized of 0.60). This assumes a nominal a = 0.025 (two-sided) accounting for two primary comparisons, each Medifast group compared to the control group, in order to maintain an overall type I error of a = 0.05. To account for possible attrition, a total sample of 198 participants (n = 66 *I* group) will be randomized.

8.2. Statistical Analysis

8.2.1. Analysis Populations

An intent-to-treat (ITT) population will include all participants who were randomized into the study. A complete case population (i.e., completers) will include the subset of participants that completed the study on their assigned intervention. A modified ITT population will include all randomized participants that had a least one post-baseline weight measurement.

All decisions regarding exclusion from the outcome populations will be documented prior to database lock.

8.2.2. Outcome Analysis

Descriptive statistics [number of participants, mean, standard error of the mean (SEM), standard deviation, median, interquartile limits, minimum and maximum] will be presented for continuous variables. Ratings for categorical variables will be presented as counts and percentages.

Baseline comparisons for demographic characteristics between control and active groups will be completed with the Chi-Square test, Fisher's exact (two-tail) tests, or analysis ofvariance (ANOVA), as appropriate.

A mixed model repeated measures analysis of covariance (ANCOVA) will be used to assess differences between study groups in continuous outcome variables. Initial ANCOVA models will contain terms for intervention, week, intervention by week interaction, and sex, with baseline measures (where applicable) as covariates. Models will be reduced using a backward selection method until only significant terms and/or intervention and baseline measures (where applicable) remain in the model. Pairwise comparisons between groups at each post-randomization visit will be conducted from the final ANCOVA model, with Dunnett's correction for multiple comparisons between each Medifast group vs. control. Assumptions of normality of residuals will be investigated for each response measurement. If the normality assumption is rejected at the I% level with the Shapiro-Wilk test (Shapiro 1965), then an analysis using ranks or other transformation will be performed.

Counts and percentages of participants who experience weight loss of :0:5% or :0:10% between baseline and each post-randomization visit will be presented. Differences between control and each active group participants with weight loss :0:5% or :0:10% will be assessed using a generalized linear model with a logit link and binomial distribution specified. Initial repeated measures models will contain terms for intervention, week, intervention by week interaction, and sex. Models will be reduced using a backward selection method until only significant terms or intervention remains **in** the model. Pairwise comparisons at each post-randomization visit will be conducted using Dunnett's correction for multiple comparisons between each Medifast group vs. control.

Counts and percentages for questionnaire responses will be presented by intervention group for ordinal outcomes (e.g. Likert scales). Differences between control and each active group will be assessed using a generalized linear model with a cumulative logit link and multinomial distribution specified. Initial repeated measures models will contain terms for intervention, week, intervention by week interaction, and sex. Models will be reduced using a backward selection method until only significant terms or intervention remains in the model. Pairwise comparisons between control and each active group at each post-randomization visit will be conducted using Dunnett's correction for multiple comparisons between each Medifast group vs. control.

8.2.3. Safety and Tolerability Analysis

Safety assessments will be determined from intervention-emergent AEs that occur after randomization at Visit 2 (week 0). Possible differences in the number of participants with at least one AE will be assessed with Chi-Square or Fisher's exact test.

Participants who achieve a BMI of 19.0 kg/m^2 or below will discontinue the weight loss diet and begin a maintenance diet and will be asked to return for remaining clinic visits. These participants will be noted in the safety analysis.

Vitals (blood pressure, pulse rate) will be summarized by group with descriptive statistics.

8.2.4. Missing or Incomplete Data

Analysis with and without imputation will be conducted in the ITT population. For the analysis with imputation, single (e.g., last observation carried forward (LOCF)], and/or multiple imputation will be considered, as appropriate (Elobeid, 2009; Peng 2015; George 2016).

9. Study Monitoring

9.1. Concomitant Medications/Supplements

All concomitant medications/supplements used for six months prior to Visit I and during the study will be reported to the study personnel for assessment and recorded in the participant's cCRF.

Use of the medications/supplements described in the "Exclusion Criteria" section and Appendix 1 is not allowed during this study. If a participant requires any of these medications, the participant may not enter the study.

9.2. Adverse Event Monitoring

In a consensus view of guidelines for the design, conduct and reporting of human intervention studies to evaluate the health benefits of foods, an International Life Sciences Institute Europe Expert Group defines an AE as "any untoward medical occurrence or undesirable clinical experience in a participant in a clinical trial, whether or not considered related to the intervention" (Welch 2011). This includes any occurrence that is new in onset or aggravated in severity or frequency from the baseline condition, or abnormal results of diagnostic procedures (including laboratory test abnormalities where applicable). Therefore, clinical observations, including responses to the question, "Have there been in any changes in your health or medications since you were last asked?" will be collected post randomization. These observations will be reviewed for assessment of AE, including severity and potential relationship to the dietary intervention as determined by the study physician.

Events should be considered AEs if they:

- Result in discontinuation from the study,
- Require treatment or any other therapeutic intervention,
- Require further diagnostic evaluation (excluding a repetition of the same procedure to confirm the abnormality),
- Are associated with clinical signs or symptoms judged by the Clinical Investigator to have a significant clinical impact.

9.2.1. Grading and Severity

The ClinicalInvestigator will evaluate all AEs with respect to their severity, and record the outcome and action taken on the AE eCRF. AEs will be graded as:

Mild:	Awareness of symptoms but easily tolerated
Moderate:	Discomfort enough to interfere with but not prevent daily activity
Severe:	Unable to perform usual activity

9.2.2. Relationship

The Clinical Investigator will also judge the likelihood that the AE was related to the diet plan administered and document this on the appropriate eCRF as:

Jason Pharmaceuticals, Inc. BI0-1607 (MED 019) 21 .June 2016; Version 1.7 Confidential

NOT RELATED	This category applies to those adverse experiences which, after careful consideration, are clearly and incontrovertibly due to extraneous causes (disease, environment, etc.).
UNLIKELY	In general, this category can be considered applicable to those experiences that after careful medical consideration at the time they are evaluated, arc judged to be, unlikely related to the study foods administered.
POSSIBLY	This category applies to those adverse experiences for which, after careful medical consideration at the time they are evaluated, a connection with the study foods administration appears possible but cannot be ruled out with certainty.
PROBABLY	This category applies to those adverse experiences that, after careful medical consideration at the time they are evaluated, are felt with a high degree of certainty to be related to the study foods.
DEFINITELY	This category applies to those adverse experiences which, the Clinical Investigator feels are incontrovertibly related to the study foods.

Appropriate therapeutic action and follow-up measures will be performed by the Clinical Investigator in accordance with good medical practice.

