6.4.2. Labeling and Packaging of Study Foods

The Sponsor will provide a total of approximately 17 weeks' worth of study foods for each participant in the TSFL and MEDD groups to cover the 16-week weight loss phase and additional study food to account for shipping time and ensure participants do not run out of food between orders. Foods dispensed at the clinic (Visit 2; week 0) will be supplied in pre-packaged kits (starter meal kits) containing multiple boxes of pre-selected study foods packaged in their original commercial packaging. The outer box of each starter meal kit will list the group kit type (TSFL or MEDD) and will have a space to write the participant's randomization number. Subsequent study foods will be home-delivered to participants, consistent with Medifast's commercial programs. Study foods will be supplied in their original commercial packaging. Medifast meal replacements and Medifast snacks come in boxes of 7 meals or snacks each; Flavors ofl-Iome are individually packaged.

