
Table 4.10  
Secondary Outcome Variable: Weight Loss Program Adherence Descriptive Statistics and P-values

Parameter		TSFL	MEDD
Meal Replacement^	Mean (SEM)	Mean (SEM)	Mean (SEM)
	Median	Median	Median
	Q1, Q3	Q1, Q3	Q1, Q3
	Min, Max	Min, Max	Min, Max
	Corr (p-value)+	0.xxx (x.xxx)	0.xxx (x.xxx)
Nutrition Support Contact	Mean (SEM)	Mean (SEM)	Mean (SEM)
	Median	Median	Median
	Q1, Q3	Q1, Q3	Q1, Q3
	Min, Max	Min, Max	Min, Max
Coaching Contact	Mean (SEM)	Mean (SEM)	
	Median	Median	
	Q1, Q3	Q1, Q3	
	Min, Max	Min, Max	
	Corr (p-value)+	0.xxx (x.xxx)	

^average meal replacement (per day) across the 16-weeks of the study

+spearman's rank-order correlation between the corresponding parameter and absolute change in body weight from baseline (Visit 2; week 0) to end of study (Visit 7; week 16)

Table 4.11  
Secondary Outcome Variable: Nutrition Support Contact P-values

Group	Parameter	Initial & Discretionary NS contact*		Initial NS contact or None**	p-value^
MEDD	% weight loss >= 5%	N (%)	N (%)	N (%)	x.xxx
TSFL	% weight loss >= 5%	N (%)	N (%)	N (%)	x.xxx

^p-values shown are generated from Fisher's exact test

\*at least two NS contacts for MEDD or at least one NS contact for TSFL

\*\*at most one NS contact for MEDD or none for TSFL

Table 5  
Summary of Subjects with at Least One Intervention-emergent Adverse Events

	Control	TSFL	MEDD	Intervention p-value*
Any Adverse Event	N (%)	N (%)	N (%)	x.xxx
Serious	N (%)	N (%)	N (%)	x.xxx
Severe	N (%)	N (%)	N (%)	x.xxx
Related to Study Treatment*	N (%)	N (%)	N (%)	x.xxx

\*p-values shown are generated from Chi-Square or Fisher's exact test, as appropriate

\* Probably or Definitely Related to Study Treatment.

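### Protocol section 9.2.2 grades AE relatedness by two different yardsticks; if the category wording is applied literally, Control is about zero by definition in the related row of SAP Table 5

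*Protocol*

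**What the plan says.** **The question put to the investigator.** The lead sentence of protocol section 9.2.2 asks the Clinical Investigator to "judge the likelihood that the AE was related to the diet plan administered". Section 9.2 likewise speaks of "potential relationship to the dietary intervention as determined by the study physician". Control has a diet plan, so both phrases cover all three arms.

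**The answer categories.** In the same section, UNLIKELY, POSSIBLY, PROBABLY and DEFINITELY all refer to the study foods. PROBABLY is for events that "are felt with a high degree of certainty to be related to the study foods"; DEFINITELY is for events that "the Clinical Investigator feels are incontrovertibly related to the study foods". Section 6.7, in describing withdrawal for an adverse event, says the category "includes all categories of study food relatedness".

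**Who gets study food.** Section 6.4.2 has the sponsor supplying about 17 weeks' "worth of study foods for each participant in the TSFL and MEDD groups". Under section 6.4.1, Control follows a self-directed food-based diet. Control completers get ordering instructions only at Visit 7.

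**The analysis.** SAP Table 5 has a related row for Control, TSFL and MEDD with a single p-value by chi-square or Fisher's exact test. Its footnote defines the row as "Probably or Definitely Related to Study Treatment". The SAP does not say what study treatment means for Control. SAP section 11.0 names a test only for participants with at least one AE; the p-value on the related row appears only in the table shell.

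**The concern.** Table 5 counts exactly the two categories that, as defined, a Control event cannot meet during the diet phase. NOT RELATED does not fit a diet-caused Control event either, because it is reserved for events with an indisputable outside cause. Such an event would tend to land in UNLIKELY, which Table 5 does not count.

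Foods and plan are not synonyms in this protocol. Section 9.2.7 separates them, treating the foods as safe in pregnancy but the calorie levels of the meal plans as unsuitable. The calorie levels also differ by arm: 800-1000 kcal/day in TSFL, 1100-1300 in MEDD, and an individual target for 7% weight loss in Control (section 6.4.1).

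At stake is the meaning of one p-value. On a literal reading, the related row could show an excess in the programs when plan-related event rates are equal, because the scale is open to two arms and closed to the third.

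**Working it through.** **1. Arm sizes.** The documents state no related-AE rate, so the only plan figures to bring in are the arm sizes (protocol section 8.1, SAP section 3.0): 198 / 3 = 66 randomized and 55 evaluable per group. The 55 reproduces. With a 9.0 lb difference, SD 15.0 lb and two-sided alpha 0.025, the normal formula gives 53 per group for 80% power, and noncentral-t power at 55 is 80.7%. Table 5 is an mITT table, so 66 is the maximum; 55 is used as a lower case.

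**2. Test.** Alpha is 0.05 two-sided (SAP section 9.0). For counts x in three arms of n, with total T and e = T/3:

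X² = Σ[(x − e)²/e + (x − e)²/(n − e)], 2 df, p = exp(−X²/2).

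Example with Control at 0 and 6 events in each program, n = 66: e = 12/3 = 4; squared deviations 16 + 4 + 4 = 24; X² = 24/4 + 24/62 = 6.387; p = 0.041. The three-arm exact test gives 0.026. With 0, 5 and 5 the chi-square p is 0.072 and the exact p is 0.0499.

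**3. Rejection probability.** Assume the same true rate r of participants with a plan-related event in every arm. On the literal reading Control is fixed at 0 and every program event is scored as food-related:

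R(r) = Σₐ Σ_b Bin(a; n, r) · Bin(b; n, r) · 1[p(0, a, b) ≤ 0.05].

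With a common yardstick, the Control count is also binomial and the sum runs over all three counts.

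| n per arm | rate r | Control fixed at 0: chi-square / exact | Common yardstick: chi-square / exact |
|---|---|---|---|
| 66 | 2% | 8.6% / 3.2% | 3.8% / 1.6% |
| 66 | 5% | 23.6% / 27.6% | 4.3% / 3.9% |
| 66 | 10% | 80.4% / 90.6% | 4.8% / 4.3% |
| 55 | 2% | 6.8% / 2.0% | 3.6% / 1.2% |
| 55 | 5% | 18.2% / 17.3% | 4.1% / 3.5% |
| 55 | 10% | 68.2% / 76.6% | 4.6% / 4.6% |

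The SAP leaves the choice between chi-square and Fisher to what is appropriate, so both are shown. The choice does not remove the problem at 5% or 10%.

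**4. Could a Control zero arise honestly?** Under a common yardstick with n = 66 its probability is (1 − r)⁶⁶: 26% at 2%, 3.4% at 5% and 0.1% at 10%. Except at low rates, a zero would be more a product of the wording than of chance.

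**5. Why these are upper figures.** A literal grader would also withhold PROBABLY and DEFINITELY from program events caused by calorie restriction rather than by the foods. If half of the program events were lost that way (an illustrative assumption), a true 10% would be recorded as 5%, and at 66 per arm the chi-square rejection rate would fall from 80.4% to 23.6%.

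**The case against.** The strongest reply is that the instruction, not the category text, governs. The lead sentence of 9.2.2 and section 9.2 both speak of the diet, section 6.5.1 calls the study a dietary intervention with no investigational product, section 9.2.5 refers to the study diet, and Table 5 refers to study treatment rather than study food. An investigator could well grade a Control event as Probably related on that basis. This stands to the extent that the Control zero follows from one of two readings. It does not clear the plan, because nothing says which reading prevails and two graders could differ.

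The size is also open to challenge. The rates are assumed. Table 5 counts only the top two categories, and section 9.2 directs that an event counts as an AE if it leads to discontinuation, treatment or further diagnostic work, or has significant clinical impact, so recorded rates may be low. At 2% the distortion is small. This stands too.

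A reader might infer that harm from the calorie level itself would go unseen. The documents do not support that: the any-AE, serious and severe rows of Table 5 count events in all arms whatever their attribution.

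A reader might also infer that the comparison of withdrawal reasons is biased. Section 6.7 does define the Adverse Event reason as an "event which results in discontinuation of the study food by the participant" or one for which the investigator requires stopping study food, which does not literally fit Control. But SAP Table 1 only lists counts and percentages, with no test, and section 10.5 allows removal for an AE in any arm. What remains is a classification gap.

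**Conclusion.** The point holds as an internal contradiction with a conditional consequence. The contradiction within section 9.2.2 is plain on the page. If the category definitions are applied literally, the three-arm p-value on the related row does not compare like with like, with false rejection well above 5% at assumed rates of 5% and 10%. Those figures rest on equal true rates, literal grading and full scoring of program events, so they are upper bounds.

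The stronger statement, that Control must score zero, goes too far. The lead sentence permits Control events to be graded as related. Even on the literal reading, a Control completer could order study food after Visit 7 and have an event within the 30-day reporting window of section 9.2.5.

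The effect is confined to one row of a secondary safety table. The other AE rows and all weight outcomes are untouched. It merits correction because the repair is nearly free.

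**What to change.** - In protocol section 9.2.2, word UNLIKELY, POSSIBLY, PROBABLY and DEFINITELY against the lead sentence's own term, the diet plan administered, stated to include any study foods, for all three arms.
- Define study treatment in the SAP Table 5 footnote in the same words.
- Reconcile the study-food wording of the Adverse Event withdrawal reason in section 6.7 with section 9.2.2, so that a Control withdrawal for an adverse event can be classified. This concerns a reporting category only and changes no stopping rule.
- If events have already been graded under the present definitions, keep the Control counts but report the related row descriptively, with a footnote explaining the yardstick and no p-value.

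The cost is a small wording amendment to the protocol and the table shell, with matching eCRF help text. No new data are needed. The downside is that Control may then show some related events.
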